4.2.1.2 Patient-reported Outcomes Endpoints

Patient-reported outcomes can provide unique information on the impact of treatment intervention from the participant's perspective as some domains are difficult to observe or are subjective and are best when collected directly from the participant. This study will include 2 PRO interviewer-administered questionnaires, the KDQOL-SF and the EQ-5D-5L, administered in a subset of study sites.

The KDQOL-SF questionnaire was developed for patients with kidney disease and those on dialysis to measure the effect of the disease on activities of daily living, work status, sexual function, sleep, and social interaction. It also captures symptoms and patient satisfaction with treatment and incorporates the SF-36 generic health-related QoL measure [Maruish, M. E. 2011], which was developed by the RAND Corporation in 1997, includes 80 items, and can be completed in approximately 16 minutes [Hays, R. D., et al 1997]. It has demonstrated good internal consistency and reliability [Barotfi, S., et al 2006]. In a review article of PRO measures in chronic kidney disease, Aiyegbusi et al. evaluated 25 measures from 66 published studies. They found strong evidence of internal and structural validity, moderate evidence of test-retest validity, and limited evidence for content validity for the KDQOL-SF, recommending this instrument for research use in patients on dialysis [Aiyegbusi, O. L., et al 2017].

The EQ-5D-5L is a generic questionnaire used to assess current health status as reported by patients and will provide data to develop health utilities for use in health economic analyses [Rabin, R. and de Charro, F. 2001]. It consists of 5 domain questions and 1 VAS response. The domain questions assess mobility, self-care, usual activities, pain/discomfort, anxiety/depression, with 5-level response options (no problems, slight problems, moderate problems, severe problems, and extreme problems). Summary scores will be calculated from the 5 domain scores according to scoring instructions from the EuroQol group and the EQ-5D-5L value sets for the US and for Europe. Scores range from 1.00 for perfect health to 0.00 for death. The EQ-5D VAS included in the EQ-5D-5L records patient self-rated health on a 20 cm vertical VAS with endpoints labeled 'the best health you can imagine' and 'the worst health you can imagine' and is scored on a 0 to 100 scale. The EQ-5D-5L is available in over 60 translations with established validity, reliability, and responsiveness

[Pickard, A. S., et al 2007] and is appropriate for a wide range of health conditions and treatments [EuroQol Research Foundation 2019]. It has been used in patients with ESRD and is a valid and sensitive health utility measure in this population [Lee, A. J., et al 2005] [Manns, B. J., et al 2002] [Gerard, K., et al 2004]. Minimally important difference estimates for the EQ-5D utility score range between 0.03 and 0.05 [McClure, N. S., et al 2018]. In cases when a validated translation is needed and not available for a specific language, participants who speak that language will be exempt from the requirement to complete the questionnaire.

The KDQOL-SF and EQ-5D-5L PROs are not pure efficacy or safety endpoints because they are affected by both disease progression and treatment tolerability.

4.2.1.3 Safety Endpoints

General safety and tolerability will be evaluated by clinical review of all relevant parameters, including AEs, vital signs, laboratory safety tests (ie, blood chemistry, hematology, pregnancy testing), and systemic infusion reaction assessment. 12-lead ECGs will be performed, and vital status assessment will be collected.

A CAC, whose members are blinded to the study-group assignments, will adjudicate all site reported bleeding AEs (See Section 10.1.4.3, Appendix 1). The secondary endpoint of time to first occurrence of ISTH major bleeds plus clinically relevant non-major bleeding events will also be evaluated.

Bleeding Endpoints

Events meeting the ISTH criteria [Schulman, S. 2005] for major bleeding or clinically relevant non-major bleeding will be reported as bleeding endpoints.

Major bleeding events have a symptomatic presentation and include the following criteria:

- 1. Fatal bleeding, and/or
- 2. Symptomatic bleeding in a critical area or organ, such as intracranial, intraspinal, intraocular, retroperitoneal, intra-articular, pericardial, intramuscular with compartment syndrome, and/or
- 3. Bleeding causing a decrease in hemoglobin level of 20 g/L or more or leading to transfusion of 2 or more units of whole blood or red cells.

Clinically relevant non-major bleeding events have signs or symptoms of hemorrhage that do not meet the criteria for major bleeding events, but do meet at least 1 of the following criteria:

- 1. Requiring medical intervention by a healthcare professional
- 2. Leading to hospitalization or increased level of care
- 3. Prompt a face-to-face evaluation by a healthcare professional

4.2.1.4 Pharmacokinetic Endpoints

The PK data from this study may be combined with data from other Phase 1 and Phase 2 studies for population PK analysis using nonlinear mixed effects modeling. The key exploratory endpoints for MK-2060 are C_{max} and C_{trough}. If data permit, estimates of population PK parameters such as CL, Vc, as well as estimates of inter-individual and residual variability will be determined. In addition, effects of demographic or laboratory factors (eg, age, race, weight, gender, renal function) on PK parameters will be assessed if possible. The results of this population PK analysis will be summarized in a separate report.

4.2.1.5 Immunogenicity Endpoints

Immunogenicity to MK-2060 will be described as the results of the ADA assay from samples taken during the double-blind treatment period.

ADA samples will be collected before the administration of study intervention at selected visits and from all participants. The incidence and magnitude (titer) of ADA positive participants and potential effects of ADA on PK, PD, and safety will be reported, as appropriate.

4.2.1.6 Pharmacodynamic Endpoints

PD endpoints that will be assessed include changes from baseline through the end of the study in FXI activity and aPTT with assays being performed at a central laboratory.

FXI activity is the most direct measure of MK-2060's efficacy in binding to FXI and FXIa and inhibiting FXIa activity.

aPTT prolongation level (relative to baseline) is an immediate measure of the antithrombotic effect of FXIa inhibition from MK-2060 and an important measure to allow comparison of MK-2060 with other FXIa inhibitors. Baseline is defined as the individual's predose aPTT value.

4.2.1.7 Planned Exploratory Biomarker Research

4.2.1.7.1 Planned Genetic Analysis

Genetic variation may impact a participant's response to therapy, susceptibility to, severity, and progression of disease. Variable response to therapy may be due to genetic determinants that impact drug absorption, distribution, metabolism, and excretion; mechanism of action of the drug; disease etiology; and/or molecular subtype of the disease being treated. Therefore, where local regulations and IRB/IEC allow, a sample will be collected for DNA analysis from consenting participants.

DNA samples may be used for research related to the study intervention(s), the disease under study, or related diseases. They may also be used to develop tests/assays including diagnostic tests related to the disease under study, related diseases, and study intervention(s). Genetic research may consist of the analysis of 1 or more candidate genes, the analysis of genetic markers throughout the genome, or analysis of the entire genome. Analysis may be conducted if it is hypothesized that this may help further understand the clinical data.

The samples may be analyzed as part of a multi-study assessment of genetic factors involved in the response to understand study disease or related conditions.

Variation across the human genome may be analyzed for association with clinical data collected in the study.

4.2.1.8 Future Biomedical Research

The Sponsor will conduct FBR on specimens for which consent was provided during this study. This research may include genetic analyses (DNA), gene expression profiling (RNA), proteomics, metabolomics (serum, plasma), and/or the measurement of other analytes, depending on which specimens are consented for FBR.

Such research is for biomarker testing to address emergent questions not described elsewhere in the protocol and will only be conducted on specimens from appropriately consented participants. The objective of collecting/retaining specimens for FBR is to explore and identify biomarkers that inform the scientific understanding of diseases and/or their therapeutic treatments. The overarching goal is to use such information to develop safer, more effective drugs/vaccines, and/or to ensure that participants receive the correct dose of the correct drug/vaccine at the correct time. The details of FBR research are presented in Appendix 6.

4.2.2 Rationale for the Use of Placebo

The purpose of this study is to evaluate the efficacy and safety of dose-ranging MK-2060 in adult participants with ESRD on hemodialysis via an AVG. A placebo-controlled study will allow for a blinded and unbiased assessment of efficacy (AVG thrombosis), safety, and tolerability. Secondary outcomes are also supported using placebo, including evaluation of

the effect of MK-2060 on bleeding risk and on time to first major thrombotic cardiovascular event.

The efficacy and safety profile of any drug is best characterized versus placebo, especially when it is being studied in a population with subjective event reporting (eg, ESRD patients receiving hemodialysis via an AVG).

4.3 Justification for Dose

4.3.1 Starting Dose for This Study

Intravenous administration of MK-2060 in participants on hemodialysis allows a simple infusion of the study intervention during hemodialysis by the treating provider with minimal disturbance to the participant. Participants will be randomized into 1 of 3 parallel treatment groups and will be treated with a fixed dose throughout the study.

The 2 IV doses of MK-2060 will be administered in parallel treatment arms, a low dose (6 mg), and a high dose (20 mg) arm, with an additional control arm (placebo). See Section 4.3.2 and Section 4.3.3 for the criteria used to select the high dose and low dose to be studied.

4.3.2 Maximum Dose/Exposure for This Study

The maximum dose used for the study is equivalent to the dose administered in the high dose arm (20 mg). Participants randomized to the high dose arm will receive this fixed dose throughout the study duration which starts with a loading phase (1 dose at dialysis on alternating days during the first week for a total of 3 doses) and is followed by a maintenance phase (1 dose each week). This high dose is projected to result in \sim 90% of participants with an Composite of the results of single ascending dose and multiple studies completed in ESRD patients receiving hemodialysis (MK-2060-P004).

The high dose (20 mg) selected for the study is below the maximum IV dose (40 mg IV x 1) tested in single-dose Phase 1 studies in normal healthy volunteers and participants with ESRD on hemodialysis. The 40 mg IV dose was well tolerated in those participants. Steady-state exposures in the high dose arm with 20 mg dosed on Day 1, Day 3, and Day 5 followed by weekly dosing are projected to have a median AUC_{0-168h} 9065 nM*hr in ESRD patients at steady state. This predicted AUC_{0-168h} is significantly below (<1%) the chronic toxicology NOAEL (AUC_{0-168h} = 1.28 x 10⁶ nM*hr from the 4-week rhesus monkey toxicity study at 60 mg/kg/week).

Since this is an event-driven study, the overall duration will depend upon the rate of recruitment and endpoint accrual. Based on the estimated recruitment and endpoint rate in the placebo arm, the median treatment duration is expected to be approximately 10 months.

4.3.3 Rationale for Dose Interval and Study Design

During Phase 1 single and multiple ascending dose testing, MK-2060 demonstrated good safety and tolerability, a steady state PK profile compatible with weekly IV dosing, and biomarker confirmation (FXI activity and aPTT) of on-target pharmacology. In this study, the dosing interval will vary between the loading phase and the maintenance phase. Employing a loading phase, with dosing on Day 1, Day 3, and Day 5 during Week 1, will achieve steady state in PK and PD within the first week as opposed to over 6 weeks with no loading phase. During the maintenance phase, study intervention will be administered once weekly on the same day each week.

The MK-2060 doses for the low (6 mg) and high dose (20 mg) arms in Phase 2 were chosen to provide a range that covers the dynamic range of PD seen with MK-2060 in the Phase 1 dose-ranging studies. The reason for choosing the MK-2060 high dose arm (20 mg) is described in Section 4.3.2. The MK-2060 low dose (6 mg) was chosen to allow for separation in the predicted PD and PK response to 6 mg dose MK-2060 relative to the responses predicted for the 20 mg MK-2060 dose. The 6 mg dose MK-2060 is projected to result in ~40% of participants with an Cmin during steady state.

4.4 Beginning and End of Study Definition

The overall study begins when the first participant (or their legally acceptable representative) provides documented informed consent. The overall study ends when the required number of AVG thrombosis are observed (unless the study stops for futility) and the last participant completes the last study-related contact, withdraws consent, or is lost to follow-up (ie, the participant is unable to be contacted by the investigator).

4.4.1 Clinical Criteria for Early Study Termination

The clinical study may be terminated early if the extent (incidence and/or severity) of emerging effects/clinical endpoints is such that the risk/benefit ratio to the study population as a whole is unacceptable. In addition, further recruitment in the study or at (a) particular study site(s) may be stopped due to insufficient compliance with the protocol, GCP, and/or other applicable regulatory requirements, procedure-related problems or the number of discontinuations for administrative reasons is too high.

Early study termination may also be considered after assessing efficacy and futility at the IA (Section 9.7).

5 STUDY POPULATION

Male/female participants of at least 18 years of age with ESRD receiving hemodialysis via an AVG will be enrolled in this study.

Prospective approval of protocol deviations to recruitment and enrollment criteria, also known as protocol waivers or exemptions, is not permitted.

Inclusion Criteria

5.1

An individual is eligible for inclusion in the study if the individual meets all of the following criteria:

Type of Participant and Disease Characteristics

- 1. Has a current diagnosis of ESRD.
- 2. Has been receiving hemodialysis (including hemodiafiltration) prescribed ≥3 times per week for a minimum of 3 hours per session via mature normally functioning (spKt/V ≥1.2), uninfected AVG. Criterion must be met for at least 75% of the sessions over the 4 weeks prior to randomization.

Demographics

3. Is male or female, ≥18 years of age inclusive, at the time of providing documented informed consent.

Female Participants

- 4. A female participant is eligible to participate if she is not pregnant or breastfeeding, and at least one of the following conditions applies: (Section 10.5.1)
 - Is not a WOCBP

OR

- Is a WOCBP and using an acceptable contraceptive method, or be abstinent from heterosexual intercourse as their preferred and usual lifestyle (abstinent on a long term and persistent basis), as described in Appendix 5 during the intervention period and for at least 90 days, corresponding to the time needed to eliminate any study intervention (eg, 5 terminal half-lives) after the last dose of study intervention. The investigator should evaluate the potential for contraceptive method failure (ie, noncompliance, recently initiated) in relationship to the first dose of study intervention.
- A WOCBP must have a negative highly sensitive pregnancy test (serum) within 6 days before the first dose of study intervention.
- The participant must be excluded from participation if the serum pregnancy result is positive.
- Additional requirements for pregnancy testing during and after study intervention are located in Section 8.3.5.

- The investigator is responsible for review of medical history, menstrual history, and recent sexual activity to decrease the risk for inclusion of a woman with an early undetected pregnancy.
- Contraceptive use by women should be consistent with local regulations regarding the methods of contraception for those participating in clinical studies.

Informed Consent

5. The participant (or legally acceptable representative) has provided documented informed consent/assent for the study. The participant may also provide consent/assent for future biomedical research. However, the participant may participate in the main study without participating in future biomedical research.

5.2 Exclusion Criteria

The participant must be excluded from the study if the participant meets any of the following criteria:

Medical Conditions

- 1. Has a recent history of cancer (<1 year). Non-melanoma skin cancers are allowed.
- 2. Has a mechanical/prosthetic heart valve.
- 3. Had a recent hemorrhagic stroke or lacunar stroke (<1 month).
- 4. Had recent evidence of bleeding requiring hospitalization or unplanned medical attention (<1 month), a history (≤2 years) of recurrent bleeding episodes including epistaxis, GI bleeds or GU bleeds requiring medical treatment or events requiring treatment with blood products.
- 5. Has a recent history of drug or alcohol abuse or dependence (<1 year).
- 6. Life expectancy <12 months.

Prior/Concomitant Therapy

7. Is currently receiving or planning to receive anticoagulants or antiplatelet medications (Individuals who plan to be on low-dose aspirin (up to 150 mg per day) during the study or require intradialytic heparin are permitted in the study).

Prohibited Medications (Section 6.5) **Oral Anticoagulants**:

- Warfarin
- Apixaban
- Dabigatran
- Rivaroxaban
- Edoxaban
- Betrixaban

IV/SC Anticoagulants:

- IV/SC Heparin and LMWH
- IV Warfarin
- IV Argatroban
- IV Bivalirudin
- IV Lepirudin
- SC fondaparinux
- IV antithrombin III

Note: Participants on medically indicated anticoagulants (other than intradialytic heparin, periprocedural heparin, or low-dose heparin for DVT prophylaxis while hospitalized) are excluded from the study (ie, participants may not discontinue prescribed anticoagulant therapy to meet study eligibility criteria in order to enroll in the study). If a participant has prior anticoagulant use, they must have discontinued the anticoagulant for 7 days prior to randomization.

Antiplatelet Medications (P2Y₁₂ inhibitor use is excluded)

- Aspirin in doses >150 mg per day (regular use)
- Clopidogrel
- Prasugrel
- Ticagrelor
- Ticlopidine

Note: Participants taking any antiplatelet agent (except for aspirin in doses ≤150 mg per day) will undergo a 7-day washout period prior to randomization. Individuals may not discontinue prescribed antiplatelet therapy to meet study eligibility criteria.

NSAIDs (eg, ibuprofen)

Note: topical NSAIDs are permitted.

Prior/Concurrent Clinical Study Experience

8. Has participated in another investigational study within 4 weeks (or 5 half-lives of the investigational drug), whichever is greater, prior to the Screening Visit. The window will be derived from the date of the last use of study treatment in the previous study.

Diagnostic Assessments

- 9. Has abnormal coagulation laboratory results including INR >2.0 and/or PT or aPTT >20% above the normal range.
- 10. Has thrombocytopenia (platelet count $<50,000/\mu$ L).
- 11. Has documented severe hypertension (SBP >200 mmHg or DBP >110 mmHg, predialysis) at screening or randomization.

Other Exclusions

- 12. Is planning on receiving a living donor renal transplant within 12 months (participants are permitted to be candidates for deceased donor renal transplants)
- 13. Is planning on receiving an AVF placement within 12 months.
- 14. Is planning non-urgent invasive dental surgeries that are liable for significant blood loss within 12 months.
- 15. Has had a hypersensitivity reaction to any component of MK-2060 drug product.

- 16. Is or has an immediate family member (eg, spouse, parent/legal guardian, sibling, or child) who is investigational site or Sponsor staff directly involved with this study.
- 17. Canada-specific criterion, see Appendix 7.

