4 STUDY DESIGN

4.1 Overall Design

This is an event-driven, randomized, placebo-controlled, parallel-group, multi-site, double-blind study of MK-2060 in participants with ESRD receiving hemodialysis via an AVG. This study is designed to evaluate the efficacy and safety of MK-2060 20 mg QW and MK-2060 6 mg QW.

During the screening period, participants will be assessed against the inclusion and exclusion criteria to select a suitable population of individuals receiving hemodialysis via a functioning AVG. Individuals using daily aspirin or heparin during dialysis are eligible; however, those using P2Y₁₂ inhibitors or systemic anticoagulants are not eligible (Section 6.5). Individuals with recent major bleeding events or at risk for future major bleeding events are excluded from participation (Section 5.2).

After a screening period of up to 30 days, approximately 489 eligible participants will be randomized in a 1:1:1 ratio and treated with MK-2060 20 mg, MK-2060 6 mg, or placebo (Section 6.1). During the loading phase on Week 1, participants will receive 1 loading dose of study intervention during 3 consecutive dialysis sessions. Starting on Week 2, participants will receive study intervention as a weekly dose of MK-2060 20 mg, MK-2060 6 mg, or placebo during their regularly scheduled dialysis session, maintaining this schedule until the required number of AVG thrombosis events is observed in the study (see Section 9.9.1). A clinical adjudication committee, whose members are blinded to the study-group assignments, will adjudicate clinical events of AVG thrombosis, bleeding, major thrombotic cardiovascular events, and death (see Section 10.1.4.3, Appendix 1). After the last treatment dose, each participant will be followed for 3 months to monitor for AEs. PROs will be completed in a subset of study sites to assess the impact of treatment intervention from the participant's perspective. Participants who undergo kidney transplant will be censored from the analysis on the date of the kidney transplant for all efficacy analyses (Section 9.6.1.1) or 3 months after the date of the kidney transplant for all safety analyses (Section 9.6.2), to avoid post-transplant events that could confound the results.

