6.5 Concomitant Therapy

Medications specifically prohibited in the exclusion criteria are not allowed during the ongoing study unless there is a clinical indication to initiate a prohibited medication. In those cases, discontinuation from study intervention may be required. The investigator should discuss any questions regarding this with the Sponsor Clinical Director. The final decision on any supportive therapy rests with the investigator and/or the participant's primary physician. However, the decision to continue the participant on study intervention requires the mutual agreement of the investigator, the Sponsor, and the participant.

Any medication (including over the counter or prescription medicines, vitamins, and/or herbal supplements or other specific categories of interest) that the participant is receiving at the time of enrollment or receives during the study must be recorded along with:

- Reason for use
- Dates of administration including start and end dates
- Dosage information including dose and frequency (route will be captured for concomitant medication taken at the time of an SAE)

Participants previously receiving intradialytic heparin to prevent clotting in the blood circuit are permitted to continue with intradialytic heparin use during the study.

The Sponsor should be contacted if there are any questions regarding concomitant or prior therapy.

PROHIBITED MEDICATIONS

Listed below are specific restrictions for concomitant therapy during the study, from providing documented informed consent to the Final Efficacy Visit (or Premature Discontinuation Visit):

Oral Anticoagulants (intradialytic heparin is permitted in the study)

- Warfarin
- Apixaban
- Dabigatran
- Rivaroxaban
- Edoxaban
- Betrixaban

IV/SC Anticoagulants:

- IV/SC Heparin and LMWH
- IV Warfarin
- IV Argatroban
- IV Bivalirudin
- IV Lepirudin
- SC fondaparinux
- IV antithrombin III

Note: Participants on medically indicated anticoagulants (other than intradialytic heparin, periprocedural heparin, or low dose heparin for DVT prophylaxis while hospitalized) are excluded from the study (ie, participants may not discontinue prescribed anticoagulant therapy to meet study eligibility criteria in order to enroll in the study). If a participant has prior anticoagulant use, they must have discontinued the anticoagulant for 7 days prior to randomization.

Antiplatelet Medications (Aspirin use up to 150 mg per day is allowed, P2Y₁₂ inhibitor use is excluded)

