- Aspirin in doses >150 mg per day (regular use)
- Clopidogrel
- Prasugrel
- Ticagrelor
- Ticlopidine

Note: Participants taking any antiplatelet agent (except for aspirin in doses \leq 150 mg per day) will undergo a 7-day washout period prior to reinitiation of study medication. Participants may not discontinue prescribed antiplatelet therapy to meet study eligibility criteria.

NSAIDs (eg, ibuprofen)

Note: topical NSAIDs are permitted.

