8.4 Adverse Events, Serious Adverse Events, and Other Reportable Safety Events

The definitions of an AE or SAE, as well as the method of recording, evaluating, and assessing causality of AE and SAE and the procedures for completing and transmitting AE, SAE, and other reportable safety event reports can be found in Appendix 3.

Adverse events, SAEs, and other reportable safety events will be reported by the participant (or, when appropriate, by a caregiver, surrogate, or the participant's legally authorized representative).

The investigator and any designees are responsible for detecting, documenting, and reporting events that meet the definition of an AE or SAE as well as other reportable safety events. Investigators remain responsible for following up AEs, SAEs, and other reportable safety events for outcome according to Section 8.4.3.

The investigator, who is a qualified physician, will assess events that meet the definition of an AE or SAE as well as other reportable safety events with respect to seriousness, intensity/toxicity and causality.

8.4.1 Time Period and Frequency for Collecting AE, SAE, and Other Reportable Safety Event Information

All AEs, SAEs, and other reportable safety events that occur after the participant provides documented informed consent but before intervention randomization must be reported by the investigator if the event causes the participant to be excluded from the study, or is the result of a protocol-specified intervention, including but not limited to washout or discontinuation of usual therapy, diet, or a procedure.

From the time of intervention and randomization through study completion, all AEs, SAEs, and other reportable safety events must be reported by the investigator.

Additionally, any SAEs brought to the attention of an investigator at any time outside of the time period specified in the previous paragraph must be reported immediately to the Sponsor if the event is considered related to study intervention.

Investigators are not obligated to actively seek AEs or SAEs or other reportable safety events in former study participants. However, if the investigator learns of any SAE, including a death, at any time after a participant has been discharged from the study, and he/she considers the event to be reasonably related to the study intervention or study participation, the investigator must promptly notify the Sponsor.

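### Exclusion 7's antiplatelet washout sentence contradicts the sentence after it, the criterion's own stem and list heading, and Section 4.1

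*Combined protocol and SAP*

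**What the plan says.** Exclusion 7 in Section 5.2 opens by excluding anyone who "Is currently receiving or planning to receive anticoagulants or antiplatelet medications", with low-dose aspirin up to 150 mg per day as the antiplatelet exception. The drug list carries the heading "Antiplatelet Medications (P2Y₁₂ inhibitor use is excluded" and names regular aspirin above 150 mg per day, clopidogrel, prasugrel, ticagrelor and ticlopidine. Two consecutive sentences follow the list:

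- The first gives an instruction: "Note: Participants taking any antiplatelet agent (except for aspirin in doses ≤150 mg per day) will undergo a 7-day washout period prior to randomization"
- The second sets a prohibition: "Individuals may not discontinue prescribed antiplatelet therapy to meet study eligibility criteria"

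Section 4.1 describes the population in the same sense as the stem and heading: "those using P2Y₁₂ inhibitors or systemic anticoagulants are not eligible".

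Section 6.5 carries a counterpart of the note among the on-study restrictions. There, users of these agents "will undergo a 7-day washout period prior to reinitiation of study medication", and a sentence against stopping prescribed antiplatelets to meet eligibility is repeated after it.

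The anticoagulant note in exclusion 7 is built differently. It excludes people on medically indicated anticoagulants, bars stopping them to qualify, and applies its 7 days only to prior use that has already ended. The opening of Section 5 rules out prospective waivers of enrollment criteria.

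**The concern.** An eligibility criterion has to give one answer for one patient. Here a single sentence sends current antiplatelet users (other than those on aspirin at 150 mg per day or less) through a washout and on to randomization. The text around it says that such a patient may not stop the drug to qualify and is not eligible.

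What is at stake is mainly patient protection and consistency between sites. A site that takes the washout sentence at face value would withdraw a prescribed antiplatelet for the sake of trial entry, which the next sentence forbids. Another site would record the same patient as a screen failure. Because waivers are not permitted, a site that notices the conflict has no prospective route round it within the protocol.

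A smaller point follows for the data. Anyone who entered this way would have had a recent change in antithrombotic cover, and the randomization strata in Section 6.3.2 record regular aspirin use only.

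**Working it through.** No sample size, alpha or event count enters, so the check is to apply each statement to each kind of patient.

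**Step 1. Patient currently on a prescribed P2Y12 inhibitor.**

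| Statement | Consequence |
|---|---|
| Washout sentence, 5.2 | Stop for 7 days, then randomize |
| Next sentence, 5.2 | May not stop in order to qualify |
| Stem of exclusion 7 | Excluded while on the drug |
| List heading, 5.2 | Excluded |
| Section 4.1 | Not eligible |

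One statement leads to randomization and four lead away from it. For this patient a washout before randomization is a discontinuation in order to qualify, so the two adjacent sentences cannot both be obeyed.

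**Step 2. Could the stem be satisfied after the washout?** A site might argue that a patient who has stopped is no longer a current user on the day of randomization. Section 8.1.2 has the criteria reviewed at both the Screening and the Randomization Visit, so the patient fails the first review. The sentence against stopping prescribed therapy closes the route in any case.

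**Step 3. Other patients the note might cover.**

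- *Regular prescribed aspirin above 150 mg per day.* The washout sentence conflicts with the next sentence and with the stem. The list heading and Section 4.1 do not settle this case, because both speak of P2Y12 inhibitors.
- *Regular non-prescribed aspirin above 150 mg per day.* The two adjacent sentences are compatible. This is the only listed item for which non-prescribed use is plausible.
- *An agent already stopped for an unrelated reason.* The washout sentence is written for people still taking the drug, so it does not literally apply, and the antiplatelet note gives no other rule for prior use. The anticoagulant note does.

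**Step 4. Could a site act on the washout sentence?** Yes. Screening lasts up to 30 days (Sections 1.3 and 8.11.1), so a 7-day washout fits and leaves 30 − 7 = 23 days. The schedule would not stop a site from carrying it out.

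**Step 5. Size.** The documents give neither the share of screened patients on these agents nor the number washed out, so no count can be computed. Section 8.1.5.1 records prior medication for 28 days before the study starts. That window contains a 7-day washout, so the sponsor should be able to count the cases.

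**The case against.** The strongest reply is that the protocol makes its intention plain. The stem, the list heading, the sentence against stopping and Section 4.1 all exclude a current P2Y12 user, and a sensible site would follow them. The second sentence can also be read as limiting the first: 7 days off the drug, but never by stopping prescribed therapy to qualify. The washout would then cover only non-prescribed aspirin above 150 mg per day, or agents stopped for another reason.

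The first half stands and limits the reach of the problem. The second half is a possible reading, but it is not written: the sentence covers every antiplatelet agent except lower-dose aspirin, addresses people still taking it, and is worded as an instruction.

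A reader might infer more than the documents support:

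- *That sites face evenly balanced opposite instructions.* They do not; four statements stand against one.
- *That the different anchor in Section 6.5 is itself an error.* That section governs therapy during the study and foresees a clinical indication to start a prohibited drug; Section 7.1 allows treatment to begin again. An interval counted to restart of study drug plausibly serves that situation. Only the repeated eligibility sentence looks out of place there.
- *That a washout after consent would begin in breach*, because Section 6.5 says "Listed below are specific restrictions for concomitant therapy during the study, from providing documented informed consent". A washout begun at consent means the drug is stopped then, so this adds little.
- *That Section 8.4.1 shows such a washout is planned*, because it mentions events from a protocol-specified intervention "including but not limited to washout or discontinuation of usual therapy". That is a general adverse event reporting clause and names no antiplatelet.
- *That a third of washed-out patients going to placebo measures harm or bias.* It restates the 1:1:1 allocation for a group of unknown size. Such patients would be randomized like any others, so no systematic difference between arms follows.

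**Conclusion.** The contradiction is real and sits inside an operative eligibility criterion. For prescribed users of the four listed P2Y12 inhibitors, the washout sentence cannot be reconciled with the sentence after it, the stem, the list heading or Section 4.1. Exclusion is the dominant reading, so the likely number of affected participants is small, but the documents give no figure. That judgment assumes that most sites read the criterion as a whole.

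The consequence is a possible withdrawal of a prescribed drug for trial entry and uneven screening between sites. It is not a threat to the primary comparison. The point should be corrected because it bears on patient safety, cannot be settled by waiver and is cheap to repair. This review takes no view on which clinical rule is right.

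**What to change.** In Section 5.2, replace the two antiplatelet sentences with one eligibility statement structured like the anticoagulant note. It should say how current use is handled, how prior use is handled, and that any interval is counted to randomization. Bring the stem, the list heading and Section 4.1 into line with whatever the sponsor decides.

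In Section 6.5, keep the on-study restart interval as a sentence of its own, and remove or reconcile the eligibility sentence that follows it.

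The cost is two reworded notes in the next amendment and a memo to sites. No procedure, sample size, event target or analysis changes. If enrollment has closed, the correction to 5.2 matters less, but the note in 6.5 still governs restarts. In either case, a listing from the prior-medication records of participants who stopped an antiplatelet shortly before randomization would show whether the sentence was ever acted on.
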